2.2 Secondary Endpoints

- 2.21 To evaluate the EOI overall response rate (ORR) for the combination of RSc+Pola+Ven in relapsed/refractory MCL.
- 2.22 To evaluate the best response (CR, PR) in patients who continue on to maintenance therapy and evaluate the improvement in the depth of response.
- 2.23 To evaluate the progression free survival (PFS) and overall survival (OS) for the combination of RSc+Pola+Ven in relapsed/refractory MCL.
- 2.24 To compare the ORR, CR, PFS, and OS in ibrutinib refractory compared to ibrutinib naïve patients.

2.25 To evaluate regimen-related toxicity for patients treated with RSc+Pola+Ven.

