22 ACCRU LY-1806

4.0 Test Schedule

	Days Prior to Registration			Induction (21-day cycles)			EOI ¹	Maintenance (12 months)	EOM ²	Post- Treatment	
Tests and Procedures	≤ 30	≤ 14		ycle ±1 d		Cycle 2 (±2 d)	Cycles 3-6 (±2 d)	After last induction	Monthly (30days)	35 days after last dose	clinical follow- up period (q3m for 2 years
	days	days	D1	D8	D15	D1	D1	dose	(±1 week) D1	(±14 days)	+/- 14 days)
Complete Medical history	X										
ECOG Performance Status	X		X	X	X	X	X	X	X	X	X
Physical exam, weight and vital signs (blood pressure, pulse, O2) ⁴	X		X	X	X	X	X	X	X	X	X
Height	X										
12-lead EKG ⁸	X										
MUGA/echocardiogram ⁸	X										
Hematology (CBC and diff)		X	X16	X	X	weekly ¹⁸	X	X	X	X	
Chemistry Labs ⁷		X	X 16	X	X	X	X	X	X	X	
Coagulation (INR, aPTT [or PTT], and PT)		X									
Serum Pregnancy test ³		X^3	X^3			X^3	X ³	X	X^3	X^3	
HIV ¹⁴ , HBV ¹³ , HCV ⁶	X										
Quantitative IgA, IgG, IgM			X					X		X	X
Optional Whole blood for MRD ¹⁷			X					X		X	
Optional Immunology Research Blood ^{12 R}			X ¹²				X ¹²	X^{12}	X ¹²		X ¹²

	Days Prior to Registration			Induction (21-day cycles) EOI ¹		Maintenance (12 months)	EOM ²	Post- Treatment clinical follow-			
Tests and Procedures	≤ 30	≤ 14	l	Cycle 1 (±1 d)		Cycle 2 (±2 d)	Cycles 3-6 (±2 d)	After last induction	(Soddys)	35 days after last dose	
	days	days	D1	D8	D15	D1	D1	dose	(±1 week) D1	(±14 days)	+/- 14 days)
Review Patient Medication Diary ¹⁵				X	X	X	X	X	X		
Optional tissue specimen R			X ¹¹					X^{11}			
Mandatory tissue specimen 19 R	X										
Concomitant medications	X					To be	recorded conti	inually until er	nd of treatment		
Adverse Event Assessment ⁵	X					To be assessed	d continually				
PET-CT scan	X							X	X ⁹	X	X ⁹
Bone marrow biopsy and aspirate	X^{10}							X^{10}			

¹ End of induction (EOI) is between 28-42 days after the last induction dose of rituximab and hyaluronidase human and polatuzumab vedotin.

² End of maintenance (EOM) visit may take place at 35 days +/- 14 days from the last dose of venetoclax treatment.

³ For women of childbearing potential only. Must be done ≤7 days prior to registration, D1 of each induction cycle, Day 1 of each maintenance cycle, and end of maintenance. Test done ≤7 days prior to cycle1 day 1 can serve as cycle 1 day 1 test.

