4.1 Survival Follow-up

	Survival Follow-up Phase ¹							
	Every 90 days until subsequent treatment or PD ² After subsequent treatment or PD ² q. 180 days Death New Primar							
Survival Follow Up	X	X	X	X	At each occurrence			

¹ If a patient is still alive 5 years after registration and they have completed protocol therapy, no further follow-up is required.

⁸ Patients with known cardiac dysfunction are required to have EKGs and assessments of left ventricular ejection fraction at screening and as clinically indicated afterwards.

⁹ PET/CT in maintenance and post treatment every 6 months or per standard of care.

¹⁰ Baseline bone marrow biopsy and aspirate can be collected within 90 days of registration if negative. However, if bone marrow is positive after most recent therapy (even if greater than 90 days prior to registration), bone marrow biopsy and aspirate does not need to be repeated, but must be recorded as positive on the pre-treatment staging. Repeat Bone Marrow biopsy only in patients who are bone marrow positive at baseline and a CR at EOI to confirm EOI CR. Repeat Bone Marrow biopsy not needed in maintenance.

¹¹ Tissue specimen optional at the end of cycle 1 and optional at the time of progression. See Section 17.0 for additional details.

¹² Draw at baseline (drawn after registration but prior to cycle 1 treatment), day 1 of cycle 3, day 1 of cycle 7, day 1 of final maintenance cycle, and one year after completion of maintenance if patient is a CR. See Section 14.0 for further details.

¹³ Screen all patients for hepatitis B (HBV) infection before initiating treatment with Rituxan. For patients who show evidence of prior hepatitis infection, consult an expert in managing hepatitis B regarding monitoring and consideration for HBV antiviral therapy before and/or during Rituxan treatment (see Section 9.5).

¹⁴ If HIV testing is done \leq 180 days prior to registration it does not need to be repeated.

¹⁵ Patients will be required to keep a medication diary for venetoclax using the diary in Appendix V. Sites will be required to upload medication diary to RAVE at the end of each cycle.

¹⁶ Hematology and chemistry will be obtained prior to administering venetoclax (predose) and 8 and 24 hours after the first dose only. Laboratory samples should be sent and analyzed immediately.

¹⁷ MRD Testing to be completed at Mayo Clinic Rochester for patients who consent to optional collection.

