11.1 Response Considerations

Schedule of Evaluations: PET/CT scans are required at baseline for all patients. For the purposes of this study, patients should be reevaluated for disease progression at the end of induction therapy and every 6 months during maintenance or per standard of care. Definitions for clinical response for patients with lymphoma are from the recently revised Cheson's et al criteria published in 2014, derived from the original criteria published in 2007. (Cheson et al, 2014) (Cheson et al, 2007). Lymph node measurements should be taken from the CT portion of the PET/CT, or other dedicated CT scans where applicable. Measurement of lymphadenopathy for purposes of assessing for PR will be determined by adding the sum of the products of the maximal perpendicular diameters of measured lesions (SPD). The PPD of a single node is sufficient to evaluate for PD (see Table 11.2). Measurable extranodal disease should be assessed in a manner similar to that for nodal disease. For these recommendations, the spleen is considered nodal disease. Disease that is only assessable (eg, pleural effusions, bone lesions) will be recorded as present or absent only, unless, while an abnormality is still noted by imaging studies or physical examination, it is found to be histologically and pathologically negative.

Response is based on PET/CT based on the revised 2014 Lugano Classification. (Cheson et al, 2014).

Progressive disease is based on either PET-CT based or CT based response criteria. PET confirmation of progressive disease is per physician discretion.

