16.32 Secondary Outcome Analysis

- 16.321 The overall response rate (ORR) at the end of induction will be estimated by the total number of patients who achieve a CR or PR by PET-CT scans according to Lugano 2014 divided by the total number of evaluable patients. All evaluable patients will be used for this analysis. Exact binomial 95% confidence intervals for the true overall response rate will be calculated. The ORR between ibrutinib-naive and ibrutinib-pretreated patients will be compared using Fisher's exact test.
- 16.322 The Best Response Rate to maintenance therapy will be evaluated. CR, PR and SD rates for patients who continue to maintenance will be estimated by number of patients who continue on maintenance therapy and achieve CR, PR or SD, respectively, at the end of maintenance divided by the total number of evaluable patients who continue to maintenance. Conversion rate from PR to CR will be evaluated by the number of patients achieving CR at EOM divided by the total number of patients who continue to maintenance in PR. Conversion rate from SD to PR or SD to CR will be evaluated by the number of patients achieving PR or CR, respectively at EOM divided by the total number of patients who continue to maintenance in SD.
- 16.323 Progression free survival (PFS) is defined as the time from registration to the earliest date of documentation of disease progression by CT or

- PET/CT or death due to any cause. The distribution of progression-free survival will be estimated using the method of Kaplan-Meier⁴. The PFS between ibrutinib-naive and ibrutinib-pretreated patients will be compared using log-rank test.
- 16.324 Overall survival (OS) is defined as the time from registration to death due to any cause. The distribution of OS will be estimated using method of Kaplan-Meier. The OS between ibrutinib-naive and ibrutinib-pretreated patients will be compared using log-rank test.
- 16.325 AEs: All eligible patients that have initiated treatment will be considered evaluable for assessing AE rate(s). The maximum grade for each type of AE from each patient will be used for analysis, and frequency tables will be reviewed to determine patterns. Additionally, the relationship of the AE(s) to the study treatment will be taken into consideration.
- 16.326 Correlative Analysis: Due to the small overall sample size, the results of these analyses will be considered exploratory and hypothesis- generating in nature.

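### Section 16.322 calls its measure a best response rate but counts only status at end of maintenance, and its SD conversion rates have empty denominators

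*Combined protocol and SAP*

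**What the plan says.** Secondary objective 2.22 reads "To evaluate the best response (CR, PR) in patients who continue on to maintenance therapy", and adds a second clause on improvement in depth of response.

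Section 16.322 is the matching analysis. It opens with "The Best Response Rate to maintenance therapy will be evaluated". The rates that follow count patients who "achieve CR, PR or SD, respectively, at the end of maintenance divided by the total number of evaluable patients" entering maintenance. For depth of response it says "Conversion rate from PR to CR will be evaluated by the number of patients achieving CR at EOM", over all patients who enter maintenance in PR. It then adds "Conversion rate from SD to PR or SD to CR will be evaluated by the number of patients achieving PR or CR" at EOM, over patients who enter maintenance in SD.

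Three other parts of the protocol bear on this:

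- **Scans during maintenance.** Section 11.1 says "patients should be reevaluated for disease progression at the end of induction therapy and every 6 months during maintenance or per standard of care". Footnote 9 to the Section 4.0 test schedule says "PET/CT in maintenance and post treatment every 6 months or per standard of care". The schedule also lists PET-CT at EOM.
- **Timing of EOM.** Footnote 2 to the same schedule says "End of maintenance (EOM) visit may take place at 35 days +/- 14 days from the last dose of venetoclax treatment".
- **Entry to maintenance.** Section 7.2 (after Table 7.2b) and Section 13.0 both send only patients in CR or PR at EOI to maintenance. Section 7.2 stops all therapy for patients who do not qualify.

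**The concern.** Best response and status at a fixed visit are different quantities whenever a response can be gained and then lost between assessments. Here an assessment before EOM is planned, so the difference can arise. The plan contains no rule that takes the best status across assessments, so the best-response clause of 2.22 has no analysis, although 16.322 carries its name. The depth clause is addressed by the PR-to-CR rate, but only through CR at EOM.

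Followed as written, EOM status would be reported as best response, and a CR gained and lost during maintenance would be left out. Section 16.6 commits to public reporting of the secondary endpoints, so the label could travel with the figure. The documents do not show what title would be used there, so little weight rests on this.

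Separately, the SD conversion rates describe a group that the protocol does not create. Either the analysis or the entry rule is misstated.

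**Working it through.** The plan states no figure for this endpoint, so there is none to reproduce. The check compares passages first, then gauges the size.

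**1. A patient traced through the rules.** PR at EOI, so the patient enters maintenance (7.2, 13.0). CR on the month-6 scan (11.1; footnote 9). Progression before EOM, so the patient moves to survival follow-up (13.0). Best response in maintenance is CR. Under 16.322 the patient is not in CR, PR or SD at EOM and is not a PR-to-CR conversion.

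**2. Direction of the error.** The conversion denominator is fixed: all patients entering in PR. Every patient in CR at EOM has reached CR in maintenance, but not the reverse. So the EOM-based rate is at most the ever-converted rate. The CR rate is affected in the same way: a patient in CR at EOI and at month 6 who progresses before EOM also drops out.

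**3. SD denominators.** Planned number entering maintenance in SD = 0. SD-to-PR and SD-to-CR are each 0/0 unless there is a protocol deviation.

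**4. Length of the unobserved interval.** Assume 12 maintenance cycles of 30 days without delay, the interim scan at day 180, and the month-12 scan taken as the EOM scan.

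- Last venetoclax dose: day 11 × 30 + 21 = 351, or day 12 × 30 = 360 if dosing runs to the end of the last cycle.
- EOM = last dose + 35 ± 14 days: day 372–400 or day 381–409.
- Interval from the interim scan: 372 − 180 = 192 to 400 − 180 = 220 days, or 381 − 180 = 201 to 409 − 180 = 229 days.

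The range is 192–229 days, about 6.3–7.5 months. A CR seen at the interim scan and lost in that interval is not counted.

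**5. Illustrative size for the conversion rate.** All rates here are assumptions. If 25–35% of the 46 evaluable patients are in PR at EOI, 0.25 × 46 = 11.5 to 0.35 × 46 = 16.1, so 12–16 patients enter in PR. Expected number missed = n × conversion rate × share of converters who lose CR before EOM.

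| Conversion | Loss before EOM | Understatement (points) | Missed, n = 12 | Missed, n = 16 |
|---|---|---|---|---|
| 20% | 10% | 2.0 | 0.24 | 0.32 |
| 20% | 25% | 5.0 | 0.60 | 0.80 |
| 35% | 10% | 3.5 | 0.42 | 0.56 |
| 35% | 25% | 8.75 | 1.05 | 1.40 |
| 50% | 10% | 5.0 | 0.60 | 0.80 |
| 50% | 25% | 12.5 | 1.50 | 2.00 |

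Eight of the 12 patient counts are below 1; the 2.0 is the extreme corner.

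**6. Rates over all maintenance patients.** The shortfall is the number entering times the share whose best status is lost by EOM. With 20–40 entering and 5–30% losing it (both assumed), that is 20 × 0.05 = 1 to 40 × 0.30 = 12 patients. This only restates the assumed loss rate; the documents offer no anchor for it.

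**7. Precision for comparison.** The exact (Clopper-Pearson) 95% interval for 8 of 16 is 24.7–75.3%.

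**The case against.** The strongest reply is that this is a labelling fault. Section 16.322 gives a numerator, a denominator and a time point, so two analysts would obtain the same number, and 2.22 sets no window for best response. Status at a common visit also has a merit that best-ever status lacks: maintenance scans may follow local practice, so a site that scans more often can record more best-ever responses. Progression after a CR is still captured by PFS (16.323). The sizes above rest on assumed rates, and the 192–229 day interval is not fixed by the protocol: a separate scan at day 360 would leave only 12–49 days before an EOM visit at day 372–409. The SD rates would simply go unreported, and no objective depends on them.

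Most of this stands as a limit on importance. The dependence on scan frequency is real and is the reason to report EOM status as well. But a reproducible number under the wrong name still leaves the stated objective without an analysis, and PFS records the later progression, not the CR that came before it. EOM may come sooner for patients who stop venetoclax early, which shortens the interval, but an earlier visit does not restore a CR already lost.

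**Conclusion.** The point holds on both parts, and neither needs an assumed figure: the analysis named for best response measures EOM status, and the SD conversion denominators are empty under the entry rule. The direction is certain, since the EOM-based conversion rate can equal or understate the ever-converted rate. The size cannot be computed from the documents. For PR-to-CR conversion it is probably small, 0.24–2.0 patients or 2–12.5 percentage points under the assumptions above, and well inside the sampling uncertainty.

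The endpoint is secondary and descriptive. The primary endpoint is CR at EOI, so the decision rule in 16.21 is unaffected. This should be corrected before analysis, so that the definition is not chosen after the data are seen, but it does not threaten the trial's main conclusion.

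**What to change.** **Preferred, to match 2.22 as written.**

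- Define best response in maintenance as the best Lugano status on any assessment after EOI through EOM, before progression or new therapy. Report EOI status as the baseline and do not count it as a maintenance response.
- Define PR-to-CR conversion as any CR in that window, divided by all patients entering maintenance in PR. Count as not converted only patients with no post-EOI response assessment, or with assessments but no CR. A CR at month 6 with no EOM scan then counts as a conversion.
- Report EOM status beside it under its own name, because best-ever status depends on how often a site scans.

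**Minimum.** Keep the 16.322 counts, rename the measure as response status at EOM, and align 2.22 with it.

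**In either case.** Reconcile the SD conversion rates with the entry rule in Sections 7.2 and 13.0, and delete them if entry remains CR or PR only. Also align the denominators: the response rates use evaluable patients, the conversion rates use patients.

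**Cost.** Wording in 16.322, and in 2.22 under the minimum repair. No visits or scans are added: PET-CT is already scheduled in maintenance and at EOM (Section 4.0), and sites already upload imaging reports at restaging (Section 18.5).

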We applied this technology to melanoma patients on an immunotherapy trial and found that non-responders had more Granzyme B+ cells and molecules than responders. Notably, these cells did not secrete the delivery molecule perforin, demonstrating our ability to deeply characterize cells. Although our most developed data is in melanoma, these assays have been performed in lymphoma. In Hodgkins lymphoma (HL), our cytokine secretion analysis demonstrated that patients who fail therapy have higher levels of IL9 (p=0.0028) and IL22 (p=0.021) at diagnosis compared to those who respond to treatment. We have also identified a suite of cytokines that increase over the course of disease treatment (including IL4, IL5, IL10; p=0.001) only in patients who fail therapy (ASH abstract 128366).

1.53 Mantle cell lymphoma international prognostic index (IPI) prognostic score is a continuous variable derived from 4 factors including age, ECOG PS, LDH and WBC count, and classifies MCL patients into 3 risk groups (low-risk, intermediate-risk, and high-risk) with differential survival (33). Other markers at diagnosis that have been shown to be prognostic in MCL are Ki-67 proliferation index (34, 35) and complex cytogenetics (36). Complex karyotype is defined as 3 or more detectable chromosomal abnormalities. Ki-67 staining performed on the tissue biopsy at diagnosis will be used to calculate the proliferation index, defined as the percentage of Ki-67 positive lymphoma cells, and to categorize patients into < 10%, 10-30% and > 30% subgroups. The MIPI score, proliferation index and complex cytogenetics status at MCL diagnosis will be correlated with the MRD rate prior to the 4th cycle of the proposed regimen. The interim MRD positivity alone and also in combination with the at-diagnosis prognostic factors will be tested for association with the treatment response at EOI according to the Lugano 2014 response criteria based on PET-CT scans.

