3.0 Patient Eligibility

For patients in the safety run in, prior to discussing protocol entry with the patient, call the ACCRU Registration Office (or email at a place on the protocol is open to the patient.

NOTE: Waivers to eligibility criteria are not allowed per ACCRU policy

- **3.1** Registration Inclusion Criteria
 - 3.11 Age \geq 18 years.
 - 3.12 Pathologically confirmed relapsed or primary refractory mantle cell lymphoma with concurrent or prior tissue sample IHC positive for cycle in D1 or that is positive for FISH or cytogenetics for t(11;14).

NOTE: Safety Portion only: MCL or indolent B cell NHL (FL (grades I-IIIa) MZL), or SLL stratified as low risk for TLS, relapsed or progressed after at least two lines of therapy, or one line of a BTK inhibitor containing therapy, or Autologous Stem Cell Transplant (AutoSCT). No limit to prior lines of therapy.

NOTE: Expansion Portion only: MCL relapsed or progressed after at least two lines of therapy, or one line of a BTK inhibitor containing therapy, or Autologous Stem Cell Transplant (AutoSCT). No limit to number of prior therapies. May have received prior BTK inhibitor therapy.

- 3.13 Measurable disease as defined with at least one lesion measuring \geq 1 x 1.5cm by PET/CT using Lugano criteria.
- 3.14 ECOG Performance Status of 0, 1, or 2. (Form is available on the ACCRU web

site under Study Resources -> Forms)

- 3.15 The following laboratory values obtained \leq 14 days prior to registration.
 - Absolute neutrophil count (ANC) ≥1000/mm³
 - Platelet count \geq 75,000/mm³
 - Hemoglobin ≥9.0 g/dL
 - International normalized ratio ≤ 1.5 x ULN for patients not receiving therapeutic anticoagulation
 - Partial thromboplastin time (PTT) or activated PTT (aPTT) $\leq 1.5 \text{ x ULN}$
 - Adequate liver function, as indicated by: AST and ALT $\leq 2.5 \times \text{ULN}$
 - Total bilirubin $< 1.5 \times ULN$ (or $\le 3 \times ULN$ for patients with documented Gilbert syndrome)
 - Adequate renal function as indicated by: calculated Cr clearance ≥45 ml/min using the modified Cockcroft-Gault formula (eCCr; with the use of ideal body mass [IBM] instead of mass):

eCCr =
$$\frac{(140 - \text{Age}) \times \text{IBM (kg)} \times [0.85 \text{ if female}]}{72 \text{ x serum creatinine (mg/dL)}}$$

Or, if serum creatinine is in µmol/L:

eCCr =
$$\frac{(140 - \text{Age}) \times \text{IBM (kg)} \times [1.23 \text{ if male, } 1.04 \text{ if female}]}{\text{serum creatinine (}\mu\text{mol/L)}}$$

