¹⁸ Subjects must return to the consenting ACCRU institution for CBC evaluation, or have outside laboratory CBC every 7 days during the first 6 weeks of therapy

¹⁹ Tissue is to be submitted no more than 30 days *after* registration. See Section 17.0 for more details.

^R Research funded

² Progressive disease is based on either PET-CT based or CT based response criteria

NOTE: A +/-14 day window is allowed for all survival follow-up visits.

5.0 Grouping Factors:

- 5.1 Cohort: Safety portion vs. expansion portion
- 5.2 Venetoclax Dosing Safety Lead-In: Dose 0 vs Dose -1
- 5.3 Previous ibrutinib exposure: ibrutinib naïve vs. ibrutinib pre-treated

NOTE: To ensure equal distribution of both ibrutinib naïve and pretreated patients at the dose level determined during the safety run-in, a minimum of 25 patients must be ibrutinib naïve. Therefore, accrual of ibrutinib pretreated patients will stop after 26 Ibrutinib pretreated patients are accrued

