12.0 Descriptive Factors

12.1 International Prognostic Index (IPI) [Shipp et al, 1993]: low risk (0 or 1 risk factors) vs. low intermediate (2 risk factors) vs. high intermediate (3 risk factors) vs. high (4 or 5 risk factors)

Risk Factors	0 points	1 point
Age	≤ 60 yrs.	> 60 yrs.
Serum LDH	≤ 1 x normal	> 1 x normal
ECOG PS	0 or 1	≥2
Stage	I or II	III or IV
Extranodal involvement	≤1 site	>1 site

Total number of risk factors = sum of the number of points for each prognostic factor.

Mantle Cell Lymphoma International Prognostic Index (Formula-based MIPI): Scores determine risk group: Low risk (<5.7) vs. Intermediate risk (≥5.7-<6.2) vs. High risk (≥6.2).

The MIPI score is calculated by this formula: $[0.03535 \times \text{age (years)}] + 0.6978$ (if ECOG > 1)+ $[1.367 \times \log_{10}(\text{LDH/ULN})]$ + $[0.9393 \times \log_{10}(\text{WBC count per }\mu\text{L})]$.

Note: The MIPI score will be calculated in Rave once the components are entered.

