16.0 Statistical Considerations and Methodology

16.1 Overview:

This is a single arm Phase II study of combination of polatuzumab vedotin, venetoclax

and rituximab and hyaluronidase human in patients with relapsed or refractory mantle cell lymphoma (MCL). The relapsed/refractory MCL patient population will include both ibrutinib-naive and ibrutinib-pretreated patients. An early safety analysis will be conducted in patients with B cell NHL who have relapsed or progressed after at least one line of therapy prior to continuing accrual in this phase II study.

16.11 Primary Endpoint: The primary endpoint of this trial is the complete response rate at the end of induction by PET-CT scans according to Lugano 2014. A complete response will be considered synonymous with "success", unless specified otherwise. All patients meeting the eligibility criteria, who have signed a consent form and have begun treatment, will be evaluable for response, unless they are determined to be a major violation.

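### PFS and OS are compared between two non-randomised ibrutinib groups by an unadjusted log-rank test with no effect size, although the prognostic MIPI is already computed

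*Combined protocol and SAP*

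**What the plan says.** Section 16.1 describes the design: "This is a single arm Phase II study of combination of polatuzumab vedotin, venetoclax" and subcutaneous rituximab. Nothing is randomised. Section 5.3 lists a grouping factor, "Previous ibrutinib exposure: ibrutinib naïve vs. ibrutinib pre-treated", with a quota: "a minimum of 25 patients must be ibrutinib naïve", and accrual of pretreated patients stops at 26. Goal 2.24 makes the comparison of PFS and OS by ibrutinib history a secondary objective, although it speaks of refractory rather than pretreated patients.

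The method for PFS (16.323) is "The PFS between ibrutinib-naive and ibrutinib-pretreated patients will be compared using log-rank test". For OS (16.324) it is "The OS between ibrutinib-naive and ibrutinib-pretreated patients will be compared using log-rank test". Apart from Kaplan-Meier estimation, nothing else is planned for these endpoints, and no Cox model or stratified test appears anywhere in the plan.

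Section 1.53 says that the MIPI "classifies MCL patients into 3 risk groups (low-risk, intermediate-risk, and high-risk) with differential survival". Section 12.0 gives its formula and adds: "The MIPI score will be calculated in Rave once the components are entered". Its planned uses are correlation with MRD and end-of-induction response (1.53) and, with other risk scores, frequency tables (16.329). The exploratory label in 16.326 is stated for the correlative analyses, not for 16.323 or 16.324.

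**The concern.** Patients fall into the two groups by treatment history, so the groups may differ in baseline prognosis. An unadjusted log-rank test cannot separate that from a difference linked to ibrutinib history, and it gives a p-value with no estimate of size. The four MIPI components are age, ECOG PS, LDH and WBC. The test schedule places ECOG PS within 30 days, and chemistry (including LDH) and CBC within 14 days, before registration. A prognostic baseline value is therefore available at no extra burden and is left out of the one analysis where it would help most.

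The background section stresses the poor outlook after progression on ibrutinib and proposes the regimen for BTK-naive or BTK-resistant patients. Readers will look at this comparison closely, even though no decision rule uses it.

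**Working it through.** **1. What the plan quantifies.** It states no power, event count, alpha or sidedness for the log-rank tests. Its only operating characteristics are for the CR rule (stop at 3 or fewer of 16; promising at 11 or more of 46). The probability of a promising result is the sum over x = 4 to 16 of P(X1 = x; 16, p) × P(X2 ≥ 11 − x; 30, p). This gives 0.0486 at p = 0.15 and 0.8506 at p = 0.35, against the stated 0.049 and 0.851. Early stopping is 0.790 and 0.134, as stated. The primary design reproduces and does not depend on this point.

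**2. Precision of the comparison.** The quota gives 25 + 26 = 51 patients. Assume two-sided 5%. By Schoenfeld, events for 80% power = (1.960 + 0.842)² / [q(1 − q)(ln HR)²], with q = 26/51 and q(1 − q) = 0.2499. For HR 2 this is 7.85 / (0.2499 × 0.4805) = 65.4, so 66 events, more than the 51 patients. HR 1.5 needs 192 events and HR 2.5 needs 38. With 40 events, power is 25%, 59% and 83% for HR 1.5, 2 and 2.5.

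**3. What a MIPI shift of 0.3 would take.** By the section 12.0 formula, 20 percentage points more patients with ECOG above 1 add 0.6978 × 0.20 = 0.140. LDH 25% higher adds 1.367 × log10(1.25) = 0.132. Together that is 0.27. Both gaps are assumptions.

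**4. Effect on the test.** Simulation, 1500 trials per scenario. Assumptions: 23 v 23 patients, exponential PFS with median 12 months, follow-up 12 to 36 months, 33 to 37 events, MIPI SD 0.6. The shift is pretreated minus naive. The rough expectation under no true effect is an apparent HR of exp(slope × shift): exp(0.15) = 1.16 and exp(0.30) = 1.35.

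| True HR | MIPI shift | Slope | Rejection, log-rank v adjusted Cox | Mean HR, unadjusted v adjusted |
|---|---|---|---|---|
| 1 | 0.3 | 0.5 | 7.8% v 6.2% | 1.17 v 1.01 |
| 1 | 0.3 | 1 | 12.3% v 5.1% | 1.32 v 1.00 |
| 2 | 0 | 1 | 40.8% v 50.7% | not recorded |
| 2 | −0.3 | 1 | 16.5% v 49.2% | 1.39 v 2.06 |

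A rerun with new code (2000 trials) agreed: 7% v 5%, 12% v 4%, 42% v 51% and 16% v 47%.

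**5. Sensitivity.** Section 16.23 expects the last patient to be followed for at least 3 years after about 2 years of accrual. With 36 to 60 months of follow-up and 23 v 23 there are about 41 to 43 events, and the log-rank false-positive rate at shift 0.3 is still 8% (slope 0.5) and 12% (slope 1). At 25 v 26 with that follow-up and slope 1 it is 14%, against 6% adjusted. With shift 0.15 and slope 1 it is 7%; with shift 0.1 and slope 0.5 it is 6%.

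**6. A different model.** Take one binary high-risk factor, 25 v 26 patients, 24 months of accrual, analysis at month 60, median 18 months in low-risk patients, no true effect and 6000 runs. With an equal risk mix the log-rank rejects in 5 to 6%. At 30% v 50% high-risk it rejects in 6%, 7% and 9% for a prognostic HR of 1.5, 2 and 3. At 25% v 65% it rejects in 8%, 15% and 25%. Stratifying by the factor holds 4.5 to 5.7% throughout. With true HR 2 and an equal mix, stratifying costs no power: 61% v 59% unadjusted at prognostic HR 2, and 61% v 52% at HR 3.

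**The case against.** The strongest case on the other side has four parts.

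- **An unadjusted comparison is a legitimate description.** Goal 2.24 and section 16.32 only say that the groups are compared. A reader might infer that the plan will present any difference as an effect of ibrutinib history. The documents do not support that: they make no causal statement and tie no decision to the result. This stands.
- **The entry criteria do not show a MIPI imbalance.** Section 3.12 admits MCL "after at least two lines of therapy, or one line of a BTK inhibitor containing therapy" or autologous transplant. It is tempting to take this as proof that the compared groups differ in the way the MIPI would correct. It concerns prior lines, which the MIPI does not contain, and any BTK inhibitor, not ibrutinib. A patient given only another BTK inhibitor could enter after that one line and still be ibrutinib-naive. This stands too.
- **An adjusted hazard ratio is not the one right answer to goal 2.24.** MIPI at registration is measured after ibrutinib exposure; ECOG PS and LDH may partly reflect failure on it, so adjustment can remove part of the difference of interest. Prior lines stay unadjusted. The movement of the unadjusted HR toward 1 in balanced groups is a marginal against a conditional quantity, not a bias in the test. These are reasons to report both results, not to omit the adjusted one.
- **The inputs are assumed.** The shift, SD and slope are not in the documents, and the 17% v 49% power contrast is the most extreme case shown. This stands, so the size is conditional.

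None of this supplies an adjustment or an effect size, and no other section does.

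**Conclusion.** The gap is real and modest. A stated secondary comparison of non-randomised groups rests on an unadjusted test with no effect size, while a score that the protocol itself calls prognostic is computed and left unused there. Under an assumed MIPI shift of 0.3 and slope of 0.5 to 1, the false-positive rate is about 8 to 12% instead of 5%. It stays near 5% if either is small. In the opposite direction the same imbalance can hide a true difference. Adjustment holds the error near 5% and, in the balanced scenarios, costs no power.

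A reader might go further and conclude that the comparison is invalid, or that MIPI adjustment would make the groups comparable. Neither follows: the unadjusted result remains a valid description, and adjustment reduces confounding without removing it. Nor is the MIPI available for everyone enrolled. It is an MCL score, the safety portion may include FL, MZL or SLL, and section 12.0 gives no time point while section 1.53 refers to scores at diagnosis. The comparison is unpowered, and the primary CR decision is untouched.

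**What to change.** In 16.323 and 16.324:

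- Keep the Kaplan-Meier curves and the log-rank test, labelled unadjusted.
- Add a pre-specified Cox model in MCL patients with ibrutinib group and the continuous MIPI calculated from registration values. Report unadjusted and adjusted hazard ratios with 95% CI side by side.
- Tabulate MIPI and number of prior lines by ibrutinib group.
- State that the adjusted result leaves prior lines unadjusted and that registration MIPI is measured after ibrutinib exposure.

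The cost is a few sentences, one extra model per endpoint and one extra parameter on a limited number of events: about 33 to 48 for PFS across the assumed scenarios, fewer for OS. No new data are needed. Fixing the covariate and its time point now also avoids choosing them after the results are seen.
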